## 2. Objectives

- **Primary Objective:** To determine if exosome-enriched culture media increases the proportion of MI oocytes maturing to MII within 4 hours compared to standard IVF media.

- **Secondary Objectives:** To assess subsequent fertilization rates, embryo quality, blastocyst development, implantation, and clinical pregnancy rates.

**3. Study Design** A prospective, single-center, randomized controlled trial. Patients will undergo standard ovarian stimulation protocols. Retrieved MI oocytes will be allocated within each patient to two different culture conditions: exosome-enriched media vs. standard media.

## 4. Study Population

- **Inclusion Criteria:**

- Women aged 35–42 years
- Undergoing IVF with antagonist protocols
- Meet at least two Bologna criteria for poor ovarian response
- Able to provide written informed consent

- **Exclusion Criteria:**

- Severe male factor infertility requiring surgical sperm retrieval
- Known untreated hydrosalpinx
- Uterine anomalies impairing implantation
- Known chromosomal abnormalities
- Participation in another investigational study within the last 3 months

## 5. Interventions

- **Control:** MI oocytes cultured in pre-equilibrated standard IVF media.
- **Intervention:** MI oocytes cultured in the same media supplemented with 10 µg/well of GMP-certified exosomes. Maturation status will be assessed at 2, 3, and 4 hours.

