## 4. Analysis Populations

- **Full Analysis Set (FAS):** All retrieved MI oocytes allocated to either exosome or standard culture conditions.
- **Per Protocol Set (PPS):** Oocytes that completed the planned culture period without protocol deviations.

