## 5. Statistical Methods

- **Primary Analysis:**
  - Compare the proportion of MI oocytes maturing to MII between exosome and standard media using chi-square or Fisher's exact tests.
- **Secondary Analyses:**
  - Compare fertilization rates and embryo quality using similar tests.
  - Implantation and clinical pregnancy rates summarized descriptively and analyzed if numbers permit.
- **Adjustment:** Logistic regression models may adjust for patient age, baseline AMH, and total gonadotropin dose.
- **Significance:** Two-sided tests,  $p<0.05$  considered statistically significant.

**6. Handling of Missing Data** Missing maturation outcomes will be treated conservatively as non-matured. Sensitivity analyses may exclude such oocytes. No imputation planned for secondary reproductive outcomes.

**7. Interim Analyses and Data Monitoring** No formal interim analyses are planned. Data will be reviewed periodically for safety and protocol compliance by the study team.

**8. Reporting Conventions** Descriptive statistics will include means, medians, standard deviations, and ranges. Tables and figures will illustrate maturation rates and embryo development outcomes by intervention.

---

End of Statistical Analysis Plan.

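### Exosomes are added per well, but oocytes are allocated and tested singly; the primary test should allow for correlation within the woman, including any shared well

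*Combined protocol and SAP*

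**What the plan says.** Three units appear in the plan.

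- **The well.** Protocol section 5 describes the intervention as the control medium "supplemented with 10 µg/well of GMP-certified exosomes". The control line reads "MI oocytes cultured in pre-equilibrated standard IVF media" and names no well layout.
- **The woman.** Protocol section 3 states: "Retrieved MI oocytes will be allocated within each patient to two different culture conditions".
- **The oocyte.** The full analysis set in SAP section 4 is "All retrieved MI oocytes allocated to either exosome or standard culture conditions". The primary analysis in SAP section 5 is to "Compare the proportion of MI oocytes maturing to MII between exosome and standard media", "using chi-square or Fisher's exact tests".

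The logistic regression in Protocol section 7 and SAP section 5 uses age, AMH and gonadotropin dose only. It has no effect for woman or well. Neither document states oocytes per well, wells per woman and medium, well volume, or whether culture is single or grouped.

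**The concern.** The treatment is defined in a unit that the rest of the plan never uses. As written, the plan allows one well per oocyte, one well per woman and medium, or a mixture. Two things follow.

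First, what an oocyte in the exosome arm is exposed to cannot be read from the documents, because that needs occupancy, volume or both.

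Second, oocytes in one well share medium, handling and neighbours. With allocation inside the woman, a shared well lies within one woman and one medium. Its effect therefore goes straight into the treatment contrast. The planned test counts such oocytes as independent. Adding a patient intercept or stratifying by patient would not help, because that removes only what a woman's two media have in common. At stake is the 5% level of the primary test.

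**Working it through.** **1. The plan's own power figure.** The inputs in SAP section 3 are 60 patients, 40% against 65%, two-sided 0.05 and power above 80%. The two-proportion formula needs 62 oocytes per medium (70 with continuity correction). Sixty per medium gives 79.0% and thirty gives 49.1%. Treated as 60 matched pairs (McNemar), power is 77.2% at within-pair correlation 0 and 81.2% at 0.1. The stated figure thus fits about one oocyte per medium per woman. That is an inference; no section caps the number of MI oocytes.

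**2. Inputs for the null calculation.** From the SAP: 60 women, 40% maturation (used in both media), two-sided 5%. Assumed, because the documents give no value: one well per medium per woman, m oocytes per well, patient correlation ρp = 0.1, and extra correlation among well-mates ρw = 0.1 to 0.3.

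**3. Formula.** Let V = p(1 − p).

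- The true variance of a woman's difference in matured counts is 2mV[1 − ρp + (m − 1)ρw].
- The pooled test uses 2mV, so its variance ratio is R = 1 − ρp + (m − 1)ρw.
- Mantel-Haenszel stratified by woman expects 2mV[1 − ρp − (m − 1)ρw/(2m − 1)], so its ratio is R divided by that bracket.
- The actual rejection rate is approximately 2Φ(−1.96/√ratio).

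Patient correlation makes the pooled test conservative and well correlation works the other way. They cancel when (m − 1)ρw = ρp.

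**4. Results.** The simulated columns are from a beta-binomial model with 4,000 replicates per setting.

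| m | ρw | Pooled ratio | Pooled, formula | Pooled, simulated | Stratified ratio | Stratified, formula | Stratified, simulated |
|---|---|---|---|---|---|---|---|
| 2 | 0.1 | 1.0 | 5.0% | 4.8% | 1.0/0.867 = 1.15 | 6.8% | 6.1% |
| 2 | 0.2 | 1.1 | 6.2% | 6.3% | 1.1/0.833 = 1.32 | 8.8% | 8.8% |
| 2 | 0.3 | 1.2 | 7.4% | 7.0% | 1.2/0.80 = 1.50 | 11.0% | 10.0% |
| 3 | 0.1 | 1.1 | 6.2% | 5.3% | 1.1/0.86 = 1.28 | 8.3% | 7.4% |
| 3 | 0.2 | 1.3 | 8.6% | 8.2% | 1.3/0.82 = 1.59 | 12.0% | 11.6% |
| 3 | 0.3 | 1.5 | 11.0% | 9.6% | 1.5/0.78 = 1.92 | 15.8% | 13.9% |

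A second simulation over the same range gave 5.7 to 9.9% for the pooled test and 7.0 to 14.7% for the stratified test.

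**5. One oocyte per well.** The pooled ratio is 1 − 0.1 = 0.9, which gives 3.9% (simulated 3.6 to 4.5%). There are no well-mates, hence no well effect.

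**6. Low mixed yield.** Assume 1, 2, 3 or 4 MI oocytes in 40, 30, 20 and 10% of women, split as evenly as possible. At ρw = 0.1/0.2/0.3 the pooled test rejects 4.3/5.0/5.4% and the stratified test 5.6/6.1/6.6%.

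**7. The remedy.** A robust variance clustered on the woman rejected 4.3 to 5.8% in every scenario of the second simulation.

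**The case against.** The strongest reply is that nothing in the documents says wells are shared. With one oocyte per well both consequences disappear, and the power figure fits about one oocyte per medium per woman. Two per well in one well per medium would mean 4 MI oocytes from each of 60 women (240 in all); three would mean 6 each (360). Protocol section 1 describes poor responders as yielding few mature oocytes. This stands: the inflation is conditional, and small at low yields.

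Three stronger readings are tempting but unsupported.

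- A reader might infer that exposure does vary and that well-mates are being counted as independent. The documents are silent on occupancy, so neither is established.
- A reader might divide 10 µg by 1, 2 or 3 oocytes (10, 5 or 3.3 µg each) and infer a three-fold dose range. That holds only if mass per oocyte drives the effect. If concentration does, and volume is constant, well-mates have the same exposure. Volume is not given.
- A reader might take the 7 to 15% as the error rate of this trial. It belongs to a patient-stratified test that the plan does not contain. It matters only because stratification is an obvious repair for patient clustering, and that repair would be more sensitive to the well than the test it replaced.

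The reply does not rescue the planned analysis. Even with single-oocyte wells, a pooled test misstates the variance of a within-woman comparison (3.6 to 4.5% instead of 5% here).

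**Conclusion.** The concern holds conditionally. It is established from the text that the amount is per well, allocation and analysis are per oocyte, occupancy and volume are unstated in both media, and the primary test ignores woman and well alike. Exposure per oocyte is therefore undefined.

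The effect on error rate depends on an occupancy and correlations that the documents do not give. At 2 to 3 oocytes per well and well correlation 0.1 to 0.3, the planned test runs from about nominal (2 per well at 0.1) to about 10%. At low mixed yield it stays at about 4 to 5.5%, and with one oocyte per well it is slightly conservative. Because one change to the analysis is valid across all these cases, the occupancy question need not be settled before correcting the SAP.

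**What to change.** **SAP section 5.** Replace the pooled chi-square or Fisher test as the primary analysis, for example:

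> *The proportion of MI oocytes reaching MII within 4 hours will be compared between media at oocyte level (difference in proportions, or logistic GEE), with a robust variance clustered on the woman and a small-sample correction. The paired within-woman difference in proportion matured will be a sensitivity analysis.*

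Clustering on the woman covers patient and shared-well correlation together, because a woman's wells lie inside her cluster. It keeps the oocyte-level proportion as the quantity estimated and retains women with one MI oocyte. A paired difference as primary would lose those women (0.40 × 60 = 24 under the yield assumed in step 6) and would weight women equally.

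**Data collection.** Record well identity and the number of oocytes in the well for every MI oocyte, in both media. Well identity that is not recorded at culture may not be recoverable later.

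**Protocol section 5.** Reconcile the per-well amount with the per-oocyte allocation in Protocol section 3 and the per-oocyte analysis in SAP sections 4 and 5. No dose or occupancy rule is proposed here.

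**Cost.** A few lines of SAP text, the well information recorded for each oocyte, and confidence intervals that may be slightly wider if wells are shared. No extra patients are needed.

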## 6. Outcome Measures

- **Primary Outcome:** Proportion of MI oocytes achieving MII maturation within 4 hours.
- **Secondary Outcomes:** Fertilization rates, day 3 embryo quality, day 5 blastocyst quality, implantation rate, and clinical pregnancy rate.

**7. Statistical Considerations** Categorical outcomes will be compared using chi-square or Fisher's exact tests. Logistic regression will adjust for

patient age, AMH, and gonadotropin dose. A p-value  $<0.05$  will be considered statistically significant.

**8. Ethical Considerations** The study will adhere to the Declaration of Helsinki and Good Clinical Practice guidelines. Ethical approval will be obtained prior to enrollment. All participants will provide written informed consent. Confidentiality will be maintained, with data anonymized using unique study codes.

**9. Data Handling and Confidentiality** Data will be stored in secure, password-protected systems. No personally identifiable information will be shared or published.

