## 2. Study Objectives and Endpoints

- **Primary Endpoint:**
  - Proportion of MI oocytes maturing to MII within 4 hours of culture.
- **Secondary Endpoints:**
  - Fertilization rate (percentage of matured MII oocytes achieving normal 2PN post-ICSI)
  - Day 3 and blastocyst embryo quality
  - Implantation rate (number of gestational sacs per embryo transferred)
  - Clinical pregnancy rate (confirmed fetal heartbeat at 8–10 weeks)

**3. Sample Size and Power** A total of 60 patients will be enrolled, based on preliminary estimates indicating that this sample size provides >80% power to detect a 25% difference in maturation rates at a two-sided alpha of 0.05, assuming maturation rates improve from ~40% (control) to ~65% (exosome group).

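### Neither the protocol nor the SAP says that whoever reads MI/MII status or grades embryos is masked to culture medium, so the primary comparison is open to expectation bias

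*Combined protocol and SAP*

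**What the plan says.** Protocol section 3 describes the trial as "A prospective, single-center, randomized controlled trial" and adds: "Retrieved MI oocytes will be allocated within each patient to two different culture conditions: exosome-enriched media vs. standard media". It carries no descriptor such as blind, masked or open-label.

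Protocol section 5 gives the reading schedule: "Maturation status will be assessed at 2, 3, and 4 hours". It does not say who reads, who prepares the wells, when the exosomes are added, or how wells are labelled.

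The primary endpoint in SAP section 2 is "Proportion of MI oocytes maturing to MII within 4 hours of culture". The secondary outcomes in protocol section 6 are "Fertilization rates, day 3 embryo quality, day 5 blastocyst quality, implantation rate, and clinical pregnancy rate", two of which are quality grades.

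Two other provisions come near the subject but do not cover it. The study codes in protocol section 8 protect participants' identity. The periodic data review in SAP section 7 is done by the study team, for safety and compliance. Neither keeps a reader from knowing the medium.

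**The concern.** The primary outcome is a call, MI or MII, made up to three times per oocyte, and the plan gives no criterion for making it. The expected direction is written into the sample size: about 40% in standard medium and about 65% with exosomes. Nothing in the plan prevents the reader from knowing which oocytes are in exosome medium. A doubtful oocyte could then be called MII more readily in one arm than in the other.

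Random allocation does not protect against this, because the error arises after allocation. The chi-square or Fisher test compares the calls as recorded. The optional logistic regression adjusts for age, AMH and gonadotropin dose. These are patient characteristics shared by both groups of oocytes from the same woman, so they cannot correct a reading that differs by medium. The day 3 and day 5 grades are exposed in the same way. A positive result could then be attributed to the reader rather than to the exosomes.

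**Working it through.** **Inputs from the documents.** Maturation 40% (control) and 65% (exosome), two-sided 5% level, 60 patients (SAP section 3); chi-square or Fisher's exact test (SAP section 5).

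**Assumptions, because the documents give no figure.** The misread rates; the number of oocytes per arm (60, that is, one per medium per patient, with 30 and 120 as a range); independent oocytes; uncorrected chi-square.

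**Step 1: the plan's own figure.** With 60 oocytes per arm and 40% against 65%, the normal approximation gives

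(0.25 − 1.96 × √(2 × 0.525 × 0.475 / 60)) / √((0.40 × 0.60 + 0.65 × 0.35) / 60) = (0.25 − 0.1787) / 0.0883 = 0.81,

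or 79.0% power. The plan claims more than 80%, so 60 per arm is a reasonable reading of it.

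**Step 2: misread model, no true effect.** Let f be the chance that an unmatured exosome oocyte is read as MII, and g the chance that a matured control oocyte is read as not MII. With a true rate of 40% in both arms:

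- apparent exosome rate = 0.40 + 0.60 f
- apparent control rate = 0.40 (1 − g)
- spurious difference = 0.60 f + 0.40 g

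The false-positive rate is the probability that chi-square gives p < 0.05, found by summing over all pairs of binomial counts at 60 per arm:

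| Misreads | Control | Exosome | Spurious points | False positives |
|---|---|---|---|---|
| None | 40% | 40% | 0 | 5.1% |
| Exosome arm only, f = 5% | 40% | 43% | 3 | 6.5% |
| Exosome arm only, f = 10% | 40% | 46% | 6 | 10.6% |
| Both arms, f = g = 5% | 38% | 43% | 5 | 8.8% |
| Both arms, f = g = 10% | 36% | 46% | 10 | 20.3% |

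For f = g = 10%, the rate is 12% at 30 oocytes per arm and 36% at 120. More oocytes make the problem worse, because the bias stays the same while the standard error shrinks.

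**Step 3: masked reading.** If the same errors fall equally on both arms, the false-positive rate stays at about 5%. Masking does not remove reading error; it stops the error from favouring one arm.

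**Step 4: a true but modest effect.** Take 40% against 50%. With f = g = 5%, the apparent rates are 0.40 × 0.95 = 38% and 0.50 + 0.50 × 0.05 = 52.5%, a difference of 14.5 points. The chance of significance rises from 19.5% to 35.6% (normal approximation).

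**Step 5: a single table.** 24/60 against 33/60 gives p = 0.100. Two more MII calls in the exosome arm (35/60) give p = 0.045. From an exact tie at 24/60, 11 extra calls are needed to reach p < 0.05.

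**Step 6: could misreads produce the planned effect?** With f = g = m, the spurious difference is 0.60 m + 0.40 m = m. A difference of 25 points would need 25% misreads in both directions.

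No comparable calculation is possible for embryo grades, because the plan gives no grading scale.

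**The case against.** The strongest reply is that silence is not evidence of unmasked reading. A reader might infer that the embryologist views sibling oocytes side by side with the medium known. The documents do not say that: they do not say who reads, how wells are labelled, or whether siblings are viewed together. The laboratory may already use codes. This stands, and it limits the point to what the plan fails to prevent.

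Second, the misread rates have no source. At 5% over-reading in the exosome arm only, the false-positive rate rises only from 5.1% to 6.5%. The 20.3% figure needs 10% errors in opposite directions in both arms at once. This also stands, and is why a range is shown.

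Third, over-reading might leave a trace. The SAP takes the fertilization rate over matured MII oocytes, so oocytes wrongly called MII would enter that denominator and could lower the exosome arm's rate. This is a partial check at best: it cannot correct the primary result, and it would be hard to tell apart from a true effect on fertilization.

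Fourth, a reader might infer that coding the wells is free because the media are prepared beforehand. The protocol uses the term pre-equilibrated for the control medium and does not say when the exosomes are added or by whom. One person might add them and later read the oocytes. Whether existing staff can divide the two tasks is not known from the documents.

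None of these replies supplies a provision for masking.

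**Conclusion.** The point holds as an omission with consequences. In the sections on design, interventions, outcomes, analysis and monitoring, nothing masks the reader of the primary outcome or the grader of embryos, and no planned analysis could remove the bias that might follow.

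The illustrated size, at 60 oocytes per arm with 5% to 10% misreads, is about 3 to 10 spurious points and a false-positive rate of roughly 6% to 20%. This rests on assumed misread rates, an assumed oocyte count and independent oocytes. Within-patient correlation would change the figures.

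It would be tempting to conclude that small misreads could manufacture the whole expected benefit. The arithmetic does not support that: misreads of this size can tip a borderline result or inflate a true effect, but the planned 25 points would need about 25% misreads in both directions. Nor do the documents show that bias will occur, only that nothing guards against it. For the embryo grades the concern applies in direction only.

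The change should be made before oocytes are read, because live readings at 2, 3 and 4 hours cannot be masked afterwards.

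**What to change.** Add to protocol section 5:

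- MI oocytes are numbered before allocation.
- Wells are labelled with a per-patient random code (for example A/B) by a member of the existing laboratory team other than the reader.
- Maturation readings and embryo grades are recorded from the code only.
- The key is held by someone other than the reader and released for analysis only after the maturation and embryo data of all patients are locked.

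If the laboratory cannot separate preparing from reading with its existing staff, the protocol should say that reading is unmasked, and the report should state this as a limitation.

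The cost is a few protocol sentences, coded labels, keeping a code key, and dividing two tasks between existing staff. If the laboratory already works this way, the cost is only that of writing it down.

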## 6. Outcome Measures

- **Primary Outcome:** Proportion of MI oocytes achieving MII maturation within 4 hours.
- **Secondary Outcomes:** Fertilization rates, day 3 embryo quality, day 5 blastocyst quality, implantation rate, and clinical pregnancy rate.

**7. Statistical Considerations** Categorical outcomes will be compared using chi-square or Fisher's exact tests. Logistic regression will adjust for

patient age, AMH, and gonadotropin dose. A p-value  $<0.05$  will be considered statistically significant.

**8. Ethical Considerations** The study will adhere to the Declaration of Helsinki and Good Clinical Practice guidelines. Ethical approval will be obtained prior to enrollment. All participants will provide written informed consent. Confidentiality will be maintained, with data anonymized using unique study codes.

**9. Data Handling and Confidentiality** Data will be stored in secure, password-protected systems. No personally identifiable information will be shared or published.

## 2. Study Objectives and Endpoints

- **Primary Endpoint:**
  - Proportion of MI oocytes maturing to MII within 4 hours of culture.
- **Secondary Endpoints:**
  - Fertilization rate (percentage of matured MII oocytes achieving normal 2PN post-ICSI)
  - Day 3 and blastocyst embryo quality
  - Implantation rate (number of gestational sacs per embryo transferred)
  - Clinical pregnancy rate (confirmed fetal heartbeat at 8–10 weeks)

**3. Sample Size and Power** A total of 60 patients will be enrolled, based on preliminary estimates indicating that this sample size provides >80% power to detect a 25% difference in maturation rates at a two-sided alpha of 0.05, assuming maturation rates improve from ~40% (control) to ~65% (exosome group).

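### Fertilization is compared only per matured MII oocyte, a denominator the medium is expected to change; a prespecified comparison per allocated MI oocyte should stand beside it.

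*Combined protocol and SAP*

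**What the plan says.** Protocol section 3 fixes the point of allocation: "Retrieved MI oocytes will be allocated within each patient to two different culture conditions". SAP section 2 then defines the endpoint on a later subset: "Fertilization rate (percentage of matured MII oocytes achieving normal 2PN post-ICSI". Under secondary analyses, SAP section 5 says "Compare fertilization rates and embryo quality using similar tests", meaning chi-square or Fisher tests as for the primary endpoint, and gives no second denominator. The protocol's own list of secondary outcomes gives no denominator for fertilization.

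Three other places bear on the point:

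- SAP section 3 plans the trial "assuming maturation rates improve from ~40% (control) to ~65% (exosome group".
- SAP section 4 defines the Full Analysis Set (FAS) as "All retrieved MI oocytes allocated to either exosome or standard culture conditions". Nothing links that set to fertilization.
- SAP section 5 adds that "Logistic regression models may adjust for patient age, baseline AMH, and total gonadotropin dose".

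SAP section 6 counts a missing maturation outcome as not matured and plans no imputation for secondary reproductive outcomes. It does not say that an oocyte which failed to mature counts as not fertilized.

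**The concern.** The denominator of the fertilization rate is formed after allocation, by the very outcome that the exosomes are meant to change. The better the primary endpoint does, the more the two sets of MII oocytes differ in make-up. A per-MII contrast then mixes two things: what the medium does to the fertilization of an oocyte that would have matured anyway, and the addition of oocytes that matured only because of the medium.

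The optional covariates do not separate the two. Age, AMH and gonadotropin dose belong to the patient. With both media used within a patient, they cannot describe which of her oocytes matured.

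What is at stake is the reading of a secondary endpoint. A lower per-MII rate with exosomes might be read as damage to the oocytes, and an equal rate as proof that fertilization is unaffected. Neither conclusion would follow.

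**Working it through.** **Inputs.** Maturation of 40% (control) and 65% (exosome) and two-sided alpha 0.05 come from SAP section 3. The documents give no fertilization rate and no number of MI oocytes per medium, so both are assumed below.

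**The plan's own figure.** SAP section 3 claims more than 80% power with 60 patients. Assume one MI oocyte per medium per patient, so n = 60 per medium, and treat the oocytes as independent. The pooled normal formula is z = [d√n − 1.96√(2p̄q̄)] / √(p₁q₁ + p₂q₂). With d = 0.25 and p̄ = 0.525 this is (1.9365 − 1.3842)/0.6837 = 0.808, so power is 79.0%; 80% needs 62 per medium. The plan's figure is approximately reproduced, and nothing below rests on it.

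**Step 1: share without a counterpart.** At most 40% of allocated oocytes would mature in either medium, so at least (0.65 − 0.40)/0.65 = 38.5% of exosome MII oocytes would not have matured in control medium. For every 60 allocated MI oocytes per medium, the fertilization denominators are 60 × 0.40 = 24 and 60 × 0.65 = 39.

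**Step 2: what equal per-MII rates allow.** Assume exosomes only add maturation. Let c and e be the per-MII rates in control and exosome medium. Among oocytes that mature either way, the rate with exosomes lies between max(0, (0.65e − 0.25)/0.40) and min(1, 0.65e/0.40). The lower limit requires as many added oocytes as possible to fertilize, the upper as few as possible. For c = e = 0.60 the limits are (0.39 − 0.25)/0.40 = 0.35 and 0.39/0.40 = 0.975. The effect on these oocytes is therefore between −25 points (every added oocyte fertilizes) and +37.5 points (none does). At other assumed common rates the range is:

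- 50%: −31.3 to +31.3 points
- 70%: −18.8 to +30 points
- 80%: −12.5 to +20 points

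These are logical limits, not expected values.

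**Step 3: illustration.** Assume in addition that oocytes maturing either way fertilize at 60% in both media, and let the added oocytes fertilize at rate f. With exosomes, per MII = (0.40 × 0.60 + 0.25f)/0.65 and per MI = 0.24 + 0.25f.

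| f (assumed) | Per MII, control vs exosome | Per allocated MI, control vs exosome |
|---|---|---|
| 40% | 60.0% vs 52.3% | 24% vs 34% |
| 60% | 60.0% vs 60.0% | 24% vs 39% |
| 80% | 60.0% vs 67.7% | 24% vs 44% |

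The signs differ only if the added oocytes fertilize less well than the others.

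**Step 4: the opposite risk.** The per-MI rate is maturation × per-MII fertilization. It shows no loss until the exosome per-MII rate falls below 0.40c/0.65, which is 30.8%, 36.9% and 43.1% for c = 50%, 60% and 70%. A uniform fall from 60% to 45% would still raise the per-MI rate from 24% to 0.65 × 0.45 = 29.25%.

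**Step 5: power of either test.** These are exact chances that chi-square gives p < 0.05, for independent oocytes. With an assumed 60 MI oocytes per medium, 24% vs 34% gives 23.3% and 24% vs 39% gives 43.3% (Fisher: 17.0% and 34.9%). The per-MII test with 24 vs 39 oocytes at 60.0% vs 52.3% gives 9.3%, against 5.2% when the rates are equal. Both comparisons serve mainly as estimates.

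**The case against.** 2PN per matured oocyte is a legitimate measure, and it fits the protocol's objective of assessing fertilization subsequent to maturation. It would not be read in isolation either. The primary endpoint is maturation per MI oocyte, and multiplying the two planned rates gives 2PN per allocated MI oocyte, provided both use the same oocytes. The added test has low power, overlaps the primary endpoint, and can hide poorer fertilization of matured oocytes. Nothing in the documents indicates that added oocytes fertilize differently from the others.

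All of this stands, and it limits the point. The information is largely there; what is absent is a prespecified comparison with an interval that allows for several oocytes per patient.

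A reader might go further and infer that a per-MII difference cannot be attributed to the medium at all. That does not follow. The per-MII rate is the ratio of two quantities measured on allocated oocytes, 2PN per MI and MII per MI. If the medium changed neither, the ratio would be the same in both media. Under random allocation a true difference is therefore caused by the medium, and only the mechanism is unresolved. A reader might also take the sign reversal in the illustration as a prediction. It depends on an assumed low rate in the added oocytes, for which the documents offer no figure.

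**Conclusion.** The point holds as a gap in a secondary analysis. At the planned maturation rates at least 38.5% of the exosome denominator lacks a control counterpart, so the per-MII comparison cannot separate an effect on fertilization competence from a change in which oocytes reach MII. Equal per-MII rates of 60% would be compatible with an effect between −25 and +37.5 points among oocytes that mature either way, though the ends need all or none of the added oocytes to fertilize.

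The 38.5% rests only on the SAP's own maturation rates. The bounds also need the assumption that exosomes only add maturation, and every fertilization rate used is assumed, so the actual size and sign of any distortion are unknown. The protection given by allocation presumes that oocytes are assigned at random; the protocol calls the trial randomized but describes no mechanism at oocyte level. The point is confined to fertilization, because the SAP gives no denominator for embryo quality. The primary endpoint and the sample size are unaffected.

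**What to change.** Add normal 2PN per allocated MI oocyte, analysed on the FAS, as a prespecified secondary comparison between media. Give it a confidence interval and use a method that accounts for several oocytes per patient. State the counting rules:

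- Oocytes that did not mature, were not injected or did not fertilize count as no.
- Missing maturation counts as not matured, as SAP section 6 already provides.
- The handling of missing 2PN results, and of oocytes that reach MII only after 4 hours, is written down.
- A sensitivity analysis excludes missing values.

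Keep 2PN per matured MII oocyte as a compared endpoint. Label it as conditional on maturation and as not isolating the medium's effect on fertilization, and say that the two results are interpreted together.

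The cost is SAP text, including the counting rules above, which are not yet written; allocation, maturation and 2PN are already planned data. The downside is one more secondary comparison with low power (about 23% to 43% in the assumed cases) that overlaps the primary endpoint and would mask reduced fertilization of matured oocytes if read alone. That is why the per-MII comparison stays.
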